- Spatial Navigation Task (version B) - delay phase - 10 minutes. Following a 30-minute delay (during which the task-switching and associative learning tasks are completed), participants will be asked to re-trace their route to a given landmark.
- Processing speed measures (Digit symbol substitution, pattern comparison, letter comparison)

13. Randomization

Randomization will occur once to determine the order of exercise conditions for the acute cross-over design, and again to determine the training groups (see Figure 1). Eligible participants will be randomized to one of two randomization groups that indicates the order of their acute exercise conditions, a separate randomization will occur to determine their exercise training group (see

Figure 1). Therefore, *all* enrolled participants complete an acute exercise assessment with both light and moderate intensity sessions (21). Following the acute exercise session, participants will continue in one of two training groups (moderate, light intensity).

When participants express interest to participate in their exercises as a couple (dyad), co-enrollment will be allowed on a limited basis. Co-enrollment means that only one of the dyad will be randomized and the partner will be automatically assigned to the same intervention group. The data for the partner then qualifies as “missing” for all analyses that depend on assumptions of random assignment. Our power analysis accounted for losing up to 15% of data due to drop out (10%) and scanner motion (5%), which would leave the sample at about 100 participants and still at strong power (~90%, two-tailed) with allowance for covariates. Based on our pilot study and adherence so far, we predict to lose less data from drop-out and motion than we initially predicted. Therefore, we will consider non-randomized partners as another source of “missing data” and set our limit for non-randomized dyads to N=6 (5%).

For participants who drop-out after randomization, we will take the following approach to determine the best type of post-testing to be done at the time of drop-out:

- First, ask them if they are still willing to do their post-test MRI and full cognitive testing sessions.
- If they cannot do all the testing, we will ask if they could do one 2-hour cognitive testing session in the lab. This would allow us to collect our learning and memory behavioral measures that tap into hippocampal function and our abbreviated battery including the RAVLT in-person.

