- However, if the drop-out participant is not willing to return to the lab for post-testing, then we will ask them if they are willing to do a brief phone survey which includes the tasks in the short battery above.

14. Neuroimaging measures

This study will utilize the 3T GE Discovery 750W MRI scanner to collect images that allow us to measure brain structure (T1, T2, diffusion), functional connectivity of brain networks sensitive to aging (resting state BOLD), neuronal metabolism (quantitative susceptibility mapping and T1ρ), and cerebrovascular reactivity (BOLD response during a breath hold paradigm). We expect to scan for one hour before each acute exercise session and 30 minutes following each acute exercise session, and for 1 hour following completion of the 6-month exercise training intervention (see outline below). In the event that a participant is uncomfortable in the scanner (e.g., wide shoulders or large head size), but would like to participate in scanning, we will prioritize T1 structural images and resting state fMRI scans which are central to testing our specific aims. Following each MRI session, images will be downloaded directly from XNAT into [BIDS](#) format. Quality control procedures will be conducted following data collection each week using [mriqc](#).

MRI scans acquired at first baseline MRI visit:

- Pre-exercise:
 - 3 x 8min resting state fMRI scans (eyes open)
 - Breath-hold task

- T1 weighted anatomical image (MPRAGE)
- T2 FLAIR anatomical image
- Post-exercise:
 - 3 x 8min resting state fMRI scans (eyes open)

MRI scans acquired at second baseline MRI visit:

- Pre-exercise:
 - 3 x 8min resting state fMRI scans (eyes open)
 - 64 Directional DTI scan to assess white matter integrity
 - T1 ρ
- Post-exercise:
 - 3 x 8min resting state fMRI scans (eyes open)

MRI scans acquired at post-training MRI visit:

- 3 x 8min resting state fMRI scans (eyes open)
- Breath-hold task
- T1 weighted anatomical image (MPRAGE)
- T2 FLAIR anatomical image
- 64 Directional DTI scan to assess white matter integrity
- T1 ρ

*Note the post-test MRI will begin in the mock MRI room with assessment of the RAVLT, oral trail-making, and the FAS word fluency tasks.

15. Research Interventions

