Both groups will wear a Heart Rate Monitor (Polar wrist watch and chest-band) during their exercise sessions. We will download HR monitor data following each session and this data will be used to give feedback on their target HR for the following session. Target HR for each condition will be based on the baseline maximal exercise test. Ratings of perceived exertion (RPE) will also be collected during the baseline max test, and in cases where there was a discrepancy between expected RPE and HR during this test, RPE will be used in conjunction with HR in developing a target HR for moderate and passive cycling sessions.

All training sessions in the first two weeks are scheduled to be in our lab. After the first two weeks, participants can do up to two sessions per week outside the lab. At the conclusion of each training session in the lab, participants are given instructions on how to complete their training at home including use of the HR monitor. In order to maintain blinding to intensity prescriptions, participants are guided to mimic the heart rate zones they are targeting in their lab sessions. For participants that live outside of a 30-mile radius, we have an additional option for more frequent home training sessions, provided that participants demonstrate they can charge and upload their HR data to Polar Flow (online) for trainer review and feedback at least once per week.

16. General Data Management/Quality Assurance

Paper/hard copy records (hard copy surveys, questionnaires, case report forms, pictures, etc.)

- Standardized procedures will be used to collect and maintain basic demographic and health data on all participants, including: (1) collecting names, email addresses, and phone numbers; (2) contacting participants with personalized letters and cards via email; (3) maintaining phone contact with participants throughout the study; (4) setting up a (secure and access-restricted) tracking file with names, email addresses, phone numbers, projected session times.
- All contact information will be stored on a secure file server and will be kept separate from study data. Once a participant has been contacted and screened with our screening session, and qualifies for the study, they will be assigned a subject number and all testing materials beyond that point will contain only the subject number.

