- All personnel involved in the study will be required to complete the training courses available for education on the protection of human research subjects provided by the University of Iowa Human Subjects Office
- All study staff will be trained in confidentiality procedures and will receive the required University of Iowa data security training.

Research procedures will collect only the minimum private information necessary to conduct the study. Measures will be taken to protect privacy throughout the study, including:

- Consent, demographic, and fitness assessment will be done in a private room
- All computerized testing will occur in either a private room or a room with computers separated by dividers
- There is no risk of loss of privacy in computerized sessions when more than one person are in the room at once, no data or performance scores are read out verbally or appear on the screen to the participant or for others to see

19. Adverse and Serious Adverse Events

Reporting all adverse events is an integral part of conducting this clinical trial. This will allow the researchers to track any occurrences of serious events and ensure they can be reviewed by the Institutional Review Board (IRB), the Data Safety Monitoring Board (DSMB), and the National Institute on Aging (NIA). The purpose of reporting adverse events is the protection and safety of the study participants. Additionally, it will provide a description and contrast of the major side effects associated with both the intervention and control groups.

Defining Adverse Events

All adverse events will be classified as either an adverse (AE) or a serious adverse event (SAE). They may occur during screening, testing, or during the administration of the intervention. Furthermore, an adverse event may or may not be related to the testing or intervention procedures.

All adverse events shall be defined as any occurrence of an adverse effect (undesirable and unintended, although not necessarily unexpected, result of the intervention); any adverse finding including a sign, symptom, or abnormal assessment or any other unfavorable outcome affects a human subject detrimentally, or that worsens, as a result of their participation in the study.

Defining Serious Adverse Events

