The most likely way in which an adverse event is identified would be when the participant reports an event to the exercise interventionists, research assistants, or research coordinator during contact time (i.e. during intervention sessions or at testing appointments).

Reporting of Adverse Events

When an adverse event is identified, the staff member identifying the adverse event will report it to the study coordinator and the principal investigator. The study coordinator will then contact the participant and an Adverse Event Report Form ([Appendix III](#)) will be completed. All adverse events that are unexpected, serious, or could affect our protocol will be electronically reported to the University of Iowa Institutional Review Board within 24 hours. If the event is not classified as a serious adverse event, it will be reported to the DSMB at the next scheduled conference call. If an event has been determined serious, reports of serious adverse events will be forwarded to the University of Iowa IRB, the DSMB, and the NIA project officer within 24-48 hours of occurrence. All adverse event documents will be stored in a separate secure cabinet by the project coordinator.

Adverse Event Flowchart

Template forms for reporting adverse events can be found in [Appendix III](#).

20. Anticipated Problems

Based on our strong preliminary data and by the PI's own recent research we believe the hypotheses will be supported. However, should this not be the case, examination of moderators and additional brain networks that interact with hippocampal-cortical systems will provide alternative approaches to testing our aims.

Recruitment:

Recruitment of older healthy adults can be a challenge. However, we are confident we can accomplish our recruitment goals by 1) advertising throughout the community with mass mailings, 2) contacting age-relevant individuals through the University of Iowa mass email system, and advertisements in the 3) daily Noon News distributed to UIHC employees, and 4) the UIHC Epic Database.

Subject Retention:

A related potential barrier is participant dropout. We will minimize dropout through careful screening, by providing ample rest and personal support between study sessions, providing personable and professional personal exercise training, and monetary compensation.

Injuries:

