Appendix III. Example Adverse Event/Serious Adverse Event Forms

Adverse Event Form										
BIKE										
Site Number: _____										
Pt ID: _____										
Has the participant had any Adverse Events during this study?  Yes  No (If yes, please list all Adverse Events below)										
Severity 1 = Mild 2 = Moderate 3 = Severe	Study Intervention Relationship 1 = Definitely related 2 = Possibly related 3 = Not related	Action Taken Regarding Study Intervention 1 = None 2 = Discontinued permanently 3 = Discontinued temporarily 4 = Reduced Dose 5 = Increased Dose 6 = Delayed Dose	Outcome of AE 1 = Resolved, No Sequel 2 = AE still present- no treatment 3 = AE still present-being treated 4 = Residual effects present-not treated 5 = Residual effects present- treated 6 = Death 7 = Unknown		Expected 1 = Yes 2 = No	Serious 1 = Yes 2 = No (If yes, complete SAE form)				
Adverse Event		Start Date	Stop Date	Severity	Relationship to Study Treatment	Action Taken	Outcome of AE	Expected?	Serious Adverse Event?	Initials
1.										
2.										
3.										

Adverse Event

Form Version 1.0

Serious Adverse Event (SAE) Report Form

Protocol Title: BIKE

Protocol Number: [Enter protocol number]

Site Number: [Enter site number]

Pt_ID: [Enter participant id]

1. SAE Onset Date: [enter SAE onset date] (dd/mmm/yyyy)

2. SAE Stop Date: [enter SAE stop date] (dd/mmm/yyyy)

3. Location of serious adverse event (e.g. at study site or elsewhere):

[Enter location of SAE]

4. Was this an unexpected adverse event?

Yes No

5. Brief description of participant with no personal identifiers:

Sex: Female Male Age: [Enter participant age]

6. Adverse Event Term(s):

[Enter adverse event terms]

7. Brief description of the nature of the serious adverse event (attach description if more space needed):

[Enter brief description of the nature of the SAE]

8. Category of the serious adverse event:

 death – date [Enter death date] (dd/mmm/yyyy)	 congenital anomaly / birth defect
 life-threatening	 required intervention to prevent
 hospitalization - initial or prolonged	permanent impairment
 disability / incapacity	 other [other category of SAE]

Serious Adverse Event (SAE) Report Form

9. Intervention type:

- Medication or Nutritional Supplement: Specify [specify text]

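### No uniform adverse-event question is scheduled and the drop-out contact names neither harms nor the reason for stopping, so harms can be under-counted and the promised arm contrast may be biased

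*Protocol*

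**What the plan says.** **Identification.** Protocol Section 19 expects an adverse event to come to light "when the participant reports an event to the exercise interventionists, research assistants, or research coordinator during contact time", and it explains contact time as "during intervention sessions or at testing appointments". This is described as the most likely route, not the only one. Once an event is identified, the coordinator contacts the participant and the adverse event form is completed. The example form in Appendix III asks "Has the participant had any Adverse Events during this study", with Yes and No boxes. Nothing says when, or to whom, that question is put.

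**Purpose.** Section 19 says of adverse event reporting that "it will provide a description and contrast of the major side effects associated with both the intervention and control groups". Neither Section 17 of the protocol nor the SAP gives a method for this.

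**Contact during training.** Section 15 plans 24 weeks at three sessions a week in both arms, all in the lab for the first two weeks. Then: "After the first two weeks, participants can do up to two sessions per week outside the lab". Participants outside a 30-mile radius may train at home more often if they upload heart-rate data for trainer review and feedback at least weekly. Section 16 mentions keeping up phone contact throughout the study, without content or frequency.

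**Contact at drop-out.** Section 13 sets three steps. "First, ask them if they are still willing to do their post-test MRI and full cognitive testing sessions". If that is not possible, one two-hour cognitive session is requested. If the person will not return to the lab, "we will ask them if they are willing to do a brief phone survey which includes the tasks in the short battery above". No step mentions adverse events or why the person stopped.

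**The concern.** When harms are learned chiefly from what participants tell staff they happen to meet, the count depends on how often they meet staff and whether they are still in the study. Both are settled after randomisation and can differ by arm. Three features of the protocol add weight:

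- The opening definition of a serious adverse event in Section 19 includes events that warrant temporary or permanent discontinuation because they are intolerable or potentially harmful (the criteria listed after it are narrower). The reason for stopping therefore bears on classification and on expedited reporting, yet the drop-out contact does not name it.
- Section 20 keeps an injured participant out of sessions until a physician consents. Session contact, the main reporting route, pauses just when there is something to report.
- Staff can observe signs only when they are present. Section 17 predicts higher heart rates at home than in the lab.

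At stake are the between-group description of side effects and what the DSMB learns about why people leave. The primary connectivity analysis is not affected.

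**Working it through.** The documents give no adverse event rate or ascertainment figure, so there is no stated number to reproduce. The check counts contacts, then shows what missed events could do to the contrast.

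**1. Lab contact (Section 15)**
- Planned sessions: 24 × 3 = 72.
- Minimum in the lab for an ordinary participant: 2 × 3 + 22 × 1 = 28.
- Maximum at home: 22 × 2 = 44, and 44/72 = 61%.
- An ordinary participant therefore still meets staff at least once every week. Beyond 30 miles no minimum is stated.

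**2. Drop-outs (Section 13)**
- Planning allowance: 10% × 120 = 12, about 6 per arm if equal. The same section now expects smaller losses, so 12 is a cautious figure.

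**3. Equal detection in both arms**
- Observed risk = true risk × share of events detected. Assume true risks of 30% (moderate) and 20% (light): risk difference 0.10, ratio 1.5.
- Detection 80% in both arms: 24% and 16%, difference 0.08, ratio 1.5.
- Detection 60% in both arms: 18% and 12%, difference 0.06, ratio 1.5.
- Equal proportional under-capture shrinks the difference and leaves the ratio alone.

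**4. Events missed among drop-outs**

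With the same assumed risks and 60 per arm, the true counts are 18 and 12. Observed risk = (true count − missed)/60.

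| Missed, moderate/light | Observed counts | Risk difference | Ratio |
|---|---|---|---|
| 0/0 | 18 and 12 | 0.10 | 1.5 |
| 6/6 | 12 and 6 | 0.10 | 2.0 |
| 9/3 | 9 and 9 | 0.00 | 1.0 |
| 12/0 | 6 and 12 | −0.10 | 0.5 |
| 0/12 | 18 and 0 | 0.30 | undefined |

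These rows assume that all 12 drop-outs had an event and that none was recorded, which is the extreme. If half did (6 missed):
- 3/3 gives 15 and 9, ratio 15/9 = 1.67.
- 6/0 gives 12 and 12, ratio 1.0.
- 0/6 gives 18 and 6, ratio 3.0.

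With assumed risks of 40% and 20% (24 and 12 events), a 12/0 split also gives 12 and 12, ratio 1.0.

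**5. Home training alone**
- Assume a true risk of 20% in both arms, capture of 90% for lab trainers and 60% for home trainers, and home shares of 30% and 60%.
- Observed: 0.20 × (0.7 × 0.9 + 0.3 × 0.6) = 16.2%, and 0.20 × (0.4 × 0.9 + 0.6 × 0.6) = 14.4%. The ratio is 1.125.
- Per 60 participants that is 9.7 against 8.6 events, about one event, even with a large assumed gap in capture.

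The drop-out route can therefore do more damage than ordinary home training. Its size and direction depend on a split by arm that the documents do not give.

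**The case against.** The best defence is that the protocol has more routes to an adverse event than the one it calls most likely. Section 18 has staff monitoring heart rate, blood pressure and exertion and documenting any level of potential event. Section 16 plans phone contact. Section 20 says what happens when an injury is reported. Each drop-out step is itself a conversation with staff, and the DSMB reviews attrition and safety. The No box in Appendix III suggests that the form may be put to everyone. The adverse event flowchart is not shown in the text available and could add detail. All of this stands, but none of it, as visible, amounts to the same question asked of everyone at the same times.

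A reader might go further and infer three things that the documents do not support:

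- *That ordinary home trainers drop out of sight.* They keep at least one lab session a week. What they lack is a scripted question. Participants beyond 30 miles may attend less often, though they have weekly trainer review.
- *That drop-outs are asked for cognitive tasks and nothing else, so they have no route into the safety record.* The first step also seeks the MRI, and the phone survey includes the battery without being limited to it. The gap is that no step names harms or the reason for stopping.
- *That the arm contrast is biased.* The home option and the reporting route are the same in both arms. Bias needs drop-out, home use or reporting to differ by arm. The different training intensities in Section 15 make that plausible, but it is not shown.

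**Conclusion.** The concern holds as a risk of under-counting, and as a possible rather than demonstrated bias in the side-effect contrast. It is clearest for drop-outs, about 12 of 120 at the planning allowance, and for participants beyond 30 miles.

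The illustrations show that a handful of missed events in arms of 60 could inflate, remove or reverse an assumed ratio of 1.5. They rest wholly on assumed event risks, on how many drop-outs had unrecorded events, and on the split by arm. They show what is possible and do not estimate what will happen. The conclusion also rests on the visible text; a missing figure could narrow the gap.

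The change is worth making because it is cheap and fits existing contacts. It does not bear on the trial's primary result.

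**What to change.** 1. Put one identical, brief adverse event question to every participant in both arms at a fixed interval, for example weekly. Ask it at the lab session or with the weekly heart-rate upload, and again at post-testing. State in Section 19 when the Appendix III form is used.
2. Add an adverse event question and the reason for stopping to every step of the drop-out contact in Section 13, including the phone survey.
3. Base the between-arm description of side effects on these solicited reports, and list events that came to light in other ways separately.
4. Reconcile Section 18, which describes training sessions as each supervised in the lab with blood pressure monitored in all of them, with the home sessions in Section 15.

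The cost is about a minute per contact and an added item at each drop-out step. More minor events will be recorded, so adverse event rates will look higher; the report should say that the events were solicited.

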Appendix III. Example Adverse Event/Serious Adverse Event Forms

Adverse Event Form										
BIKE										
Site Number: _____										
Pt ID: _____										
Has the participant had any Adverse Events during this study?  Yes  No (If yes, please list all Adverse Events below)										
Severity 1 = Mild 2 = Moderate 3 = Severe	Study Intervention Relationship 1 = Definitely related 2 = Possibly related 3 = Not related	Action Taken Regarding Study Intervention 1 = None 2 = Discontinued permanently 3 = Discontinued temporarily 4 = Reduced Dose 5 = Increased Dose 6 = Delayed Dose	Outcome of AE 1 = Resolved, No Sequel 2 = AE still present- no treatment 3 = AE still present-being treated 4 = Residual effects present-not treated 5 = Residual effects present- treated 6 = Death 7 = Unknown		Expected 1 = Yes 2 = No	Serious 1 = Yes 2 = No (If yes, complete SAE form)				
Adverse Event		Start Date	Stop Date	Severity	Relationship to Study Treatment	Action Taken	Outcome of AE	Expected?	Serious Adverse Event?	Initials
1.										
2.										
3.										

Adverse Event

Form Version 1.0

Serious Adverse Event (SAE) Report Form

Protocol Title: BIKE

Protocol Number: [Enter protocol number]

Site Number: [Enter site number]

Pt_ID: [Enter participant id]

1. SAE Onset Date: [enter SAE onset date] (dd/mmm/yyyy)

2. SAE Stop Date: [enter SAE stop date] (dd/mmm/yyyy)

3. Location of serious adverse event (e.g. at study site or elsewhere):

[Enter location of SAE]

4. Was this an unexpected adverse event?

Yes No

5. Brief description of participant with no personal identifiers:

Sex: Female Male Age: [Enter participant age]

6. Adverse Event Term(s):

[Enter adverse event terms]

7. Brief description of the nature of the serious adverse event (attach description if more space needed):

[Enter brief description of the nature of the SAE]

8. Category of the serious adverse event:

 death – date [Enter death date] (dd/mmm/yyyy)	 congenital anomaly / birth defect
 life-threatening	 required intervention to prevent
 hospitalization - initial or prolonged	permanent impairment
 disability / incapacity	 other [other category of SAE]

Serious Adverse Event (SAE) Report Form

9. Intervention type:

- Medication or Nutritional Supplement: Specify [specify text]
- Device: Specify: [specify text]
- Surgery: Specify: [specify text]
- Behavioral/Life Style: Specify: [specify text]

10. Relationship of event to intervention:

- Unrelated (clearly not related to the intervention)
- Possible (may be related to intervention)
- Definite (clearly related to intervention)

11. Was study intervention discontinued due to event? Yes No

12. What medications or other steps were taken to treat serious adverse event?

[Medications or other steps were taken to treat SAE]

13. List any relevant tests, laboratory data, history, including preexisting medical conditions

[List any relevant tests, lab data, history, including preexisting medical conditions]

14. Type of report:

- Initial
- Follow-up
- Final

Signature of Principal Investigator: [Signature of PI] Date: [sign date] (dd/mmm/yyyy)
